8 INVESTIGATIONAL PLAN

8.1 Overall Study Design and Plan

This open label outpatient extension study is designed to evaluate the long-term safety, tolerability of amifampridine in patients diagnosed with MuSK-MG and AChR-MG. In addition, evaluation of the effects of amifampridine on the MG-ADL score will be made. The study will enroll those patients who have completed the MSK-002 study and after all final evaluations for that study have been completed, or those who demonstrated benefit after completing the dose titration period but failed to meet the randomization criteria on Day 0 of MSK-002.

The duration of participation for each patient is expected to be at least 9 months as patients may continue in the study until amifampridine is approved by Regulatory Agencies or the clinical development of amifampridine is terminated for this indication. In addition to amifampridine, patients will continue to receive previous concomitant medications, as needed.

After a new informed consent is signed and inclusion / exclusion criteria for the current protocol are satisfied, eligible patients will be given the optimal dose and dosing schedule that was identified in the Run-in Period from Protocol MSK-002.

The findings from the physical exam (including vital signs, weight); 12-lead ECG; clinical laboratory test results (including pregnancy testing) and any ongoing adverse events will be used as the baseline for the Long-Term safety evaluation.

The only efficacy measurement is the MG-ADL which will be completed every 3 or 6 months. Safety and tolerability assessments will be made every 3 or 6 months or more frequently at the discretion of the Investigator. The study will continue until amifampridine is approved by Regulatory Agencies or until development of the product for this indication is halted. The Investigator may alter the dose and dosing frequency during the Long-Term Study as well as schedule additional clinic visits for any reason.

Patients will be seen in the clinic at the end of Months 3, 6, 9, 12, 15, 21, 27, 33 and 39 as detailed in the Schedule of Assessments in [Table 1](#) and Section 11. In between the 3-or 6-month visits, patients may also have telephone/video contact with the site, or unscheduled visits, if needed.

Any unused medication must be brought back to the clinic at each visit for drug accountability, and an additional supply will be dispensed.

Table 1 Schedule of Events

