8.6.4 Pregnancy Testing

Female patients of childbearing potential will have a urine pregnancy test at the end of the double blind period on Day 10 and at other time points specified in the Schedule of Events ([Table 1](#)) and in Section 11. Female patients with a positive pregnancy test at end of the double-blind study are not eligible for enrollment. Additional pregnancy tests will be performed at any visit in which pregnancy status is in question.

Refer to Section [9.4](#) for details on the reporting procedures to follow in the event of pregnancy.

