In general, all categories that appear on the CRF and in summary table templates will be reported even if no patients reported that category (e.g., if there are no patients of a particular race). The “Missing” category displayed for categorical variables in summary table templates will only be displayed if missing observations are present. If no observations meet the criteria for inclusion in a data display (e.g., if there are no SAEs), the table or listing will be generated with a line in the body of the listing such as “None reported.”

No imputation will be conducted for the missing data.

3.1.4 *Sub-group Analyses*

All safety endpoints will be analyzed by MG type: MuSK-MG and AChR-MG.

3.2 *Subject Disposition, Demographics, Baseline Characters and Study Drug Compliance*

3.2.1 *Patient Disposition*

Study completion status will be summarized for all patients. The duration of treatment will be summarized for treated patients. Categories summarized will include patients who were planned, screened, screen failure, enrolled, received study drug, completed the study, were lost to follow-up, or withdrew early. Reasons for screen failure and withdrawal will be summarized.

3.2.2 *Protocol Deviations*

Individual protocol deviations will be presented in a data listing.

3.2.3 *Demographics and Baseline Characters*

Demographic characteristics of all patients enrolled will be summarized descriptively. The summary will include age, gender, race/ethnicity, height, weight.

3.2.4 *Study Drug Exposure*

The treatment duration (day), the total dose (mg) of study drug administered, average daily dose of study drug, and study drug compliance (%) will be tabulated.

- Treatment Duration (day) is calculated as The Last Dose Date – The First Dose Date +1. If the last dose date is missing, then the last visit date will be used.
- Total Dose (mg) will be calculated as the sum of the daily dose (mg) over the Treatment Duration, considering different doses during individual time periods within the study, as documented in the IP Accountability eCRF page.
- Average Daily Dose (mg) will be calculated as Total Dose (mg) / Treatment Duration (day). This will be calculated considering each time period and Daily dose during that period, as documented in the IP Accountability eCRF page.
- Study Drug Compliance (%): $100 \times \text{Total Dose Taken (mg)} / \text{Total Dose Prescribed (mg)}$

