3.3 Safety Analysis

3.3.1 *General*

All safety summaries will be presented overall for the safety population. The evaluation will take into account the recorded adverse events (AE), clinical laboratory tests, vital signs, physical exam, ECG assessments and concomitant medications.

3.3.2 *Adverse Events*

Since patients started taking study medication before enrolled the study, all AE reported are considered as treatment-emergent adverse events (TEAE).

Tabular summaries will be provided by indication for the number and percentage of patients with:

- Any TEAE by SOC and PT. This summary will include the number of unique events reported.
- Any study drug-related TEAE by SOC and PT
- Any TEAEs by SOC, PT and maximum severity
- Any treatment-emergent serious adverse event (TESAE) by SOC and PT
- Any TEAE that results in patient discontinuation from the study by SOC and Preferred Term (PT)

A listing of all adverse events will be provided. In addition, separate data listings will be presented for the following:

- Patient deaths

- Serious Adverse Events (SAEs)
- Listing of Grade 3 (Severe) or Grade 4 (Life-threatening) AEs
- Listing of AEs leading to study discontinuation

3.3.3 *Vital Signs*

A summary of values and changes from Baseline will be provided by vital signs parameter and visit of at 3, 6, 9, 12, 15, 21, 27, 33 and 39 months.

3.3.4 *Electrocardiogram (ECG)*

Each over-read ECG interval and change from baseline in each interval will be summarized descriptively by visit at 3, 6, 9, 12, 15, 21, 27, 33 and 39 months

Treatment-emergent cardiac abnormalities, as well as the overall interpretation, will be summarized. Treatment-emergent ECG findings considered by the investigator to be clinically significant will be presented only in a listing.

3.3.5 *Clinical Laboratory Assessments*

A summary of laboratory values and changes from Baseline will be provided by test and visit of at 3, 6, 9, 12, 15, 21, 27, 33 and 39 months. In addition, laboratory measures out of range or abnormal will be presented for each visit. Values deemed clinically significant by the Investigator will not be summarized, but will be presented in a listing.

3.3.6 *Physical Examinations*

The number and percent of patients with physical examination abnormalities will be summarized by body system and visit of at 3, 6, 9, 12, 15, 21, 27, 33 and 39 months.

3.3.7 *Concomitant Medications*

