3.6 Change to Planned Protocol Analysis

In a randomized, placebo-controlled MSK-002 study, amifampridine phosphate was not effective in demonstrating a difference over placebo in MG-ADL score change from Day 0 (Baseline) to Day 10. Based on the sponsor decision, no statistical analysis will be conducted for the efficacy endpoint, change from baseline in MG-ADL score.

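### The SAP does not separate entrants by MSK-002 group, so, if baseline is MSK-003 entry, changes in vital signs and ECG mix off-drug and on-drug starting values

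*SAP*

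**What the plan says.** **Preceding study.** SAP 3.6 reports: "In a randomized, placebo-controlled MSK-002 study, amifampridine phosphate was not effective in demonstrating a difference over placebo", on MG-ADL change from Day 0 to Day 10. Protocol 8.6.4 places a "urine pregnancy test at the end of the double blind period on Day 10".

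**Who enters.** Protocol 8.1: "The study will enroll those patients who have completed the MSK-002 study". There is no restriction by arm. The same sentence also admits patients who benefited in titration but failed the Day 0 randomisation criteria.

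**Treatment at entry.** Protocol 8.1: "eligible patients will be given the optimal dose and dosing schedule that was identified in the Run-in Period from Protocol MSK-002".

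**How safety is displayed.** SAP 3.1.4: "All safety endpoints will be analyzed by MG type: MuSK-MG and AChR-MG". SAP 3.3.1 otherwise presents safety overall. No table or listing title in SAP 4.1 or 4.2 mentions MSK-002 arm. SAP 3.3.2 counts every AE as treatment-emergent, with the reason "Since patients started taking study medication before enrolled the study".

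**Baseline.** SAP 3.1.2 uses the screening visit after consent. SAP 3.5 uses Day 1 or before the first dose of study drug. Protocol 11.1 says Day 0 procedures can serve, and the asterisked footnote to protocol Table 1 lets screening data come from MSK-002.

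**The concern.** Patients who had just spent the double-blind period on placebo and patients who had just spent it on amifampridine start MSK-003 from different exposures. For the first group, a change from an entry value runs from off drug to on drug. For the second, it runs from on drug to on drug. Averaged together, the change describes neither group, and any effect on heart rate, blood pressure or ECG intervals looks smaller than it is. Protocol 6.2 lists palpitations and QTc prolongation among the clinically significant events seen with the drug, so these summaries bear on the primary objective.

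Tolerability raises a related question. An event soon after entry may reflect resuming the drug or continued treatment. The planned outputs do not identify the patient's MSK-002 group, so a reader cannot tell which.

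**Working it through.** The plan states no power, effect size or allocation ratio on this point, so there is no figure to reproduce. The check is a text trace followed by arithmetic on declared assumptions.

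**1. Do ex-placebo patients resume drug at entry?** Three statements combine: MSK-002 was placebo-controlled from Day 0 to Day 10 (SAP 3.6, protocol 8.6.4); completers enter whatever their arm (protocol 8.1); all entrants receive their Run-in dose (protocol 8.1). Together they imply that the placebo arm had about 10 days off drug and then resumes. No sentence says so, and any gap between the studies is not described. The drug status at entry of the never-randomised patients is not stated either.

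**2. Which baseline applies?** I read both SAP definitions as MSK-003 entry, and protocol 13.7 says the SAP prevails where the analysis text differs. On that reading the mixing occurs, and it does so at every visit to Month 39, because the same entry value is subtracted each time. If Day 0 in protocol 11.1 means MSK-002 Day 0 (after Run-in, before the double-blind period) and those values are used, the two randomised arms share an on-drug starting point and the mixing largely disappears.

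**3. Size of the dilution under an entry baseline.** Let f be the ex-placebo share, D the mean change in resumers and C the mean change in all others.

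- Pooled mean change = f × D + (1 − f) × C.
- With C = 0 (assumed), this is f × D.
- With f = 1/3 to 1/2 (assumed), the pooled mean is 1/3 to 1/2 of D.

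**4. Effect on whole-study AE incidence.** As a scale, 10 days is 10/91 = 11% of the time to the Month 3 visit but 10/1187 = 0.8% of the time to Month 39. Long-term incidence is therefore little affected. SAP 3.3.2 and T06 to T10 include no AE summary by time interval.

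**5. How precise would a split be?** Planned size is up to about 60 MuSK-MG and about 10 AChR-MG patients (protocol synopsis). Assume equal groups and early AE rates of 40% in resumers against 10% or 20% in continuers. The 95% half-width is 1.96 × √[p₁(1 − p₁)/n + p₂(1 − p₂)/n].

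| Group size (assumed) | 40% v 10% | 40% v 20% |
|---|---|---|
| MuSK-MG, 30 v 30 (all randomised) | ±21 points | ±23 points |
| MuSK-MG, 18 v 18 (40% of 60 never randomised) | ±27 points | ±29 points |
| AChR-MG, 5 v 5 | ±50 points | ±55 points |

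For example, with 30 per group and 40% v 10%: 1.96 × √(0.24/30 + 0.09/30) = 1.96 × 0.105 = 0.206. For a difference in mean change, 1.96 × √(2/n) gives about ±0.51 SD with 30 per group and ±0.65 SD with 18.

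**The case against.** The strongest reply is that the omission contradicts nothing in the plan and undermines no stated objective. The objective is long-term safety, the study is descriptive with no hypothesis testing, and about 10 days on placebo matters little over 39 months. Patient-level AE, vital-sign and ECG listings are already planned (DL06a, DL08, DL09). The vital-sign and ECG argument depends on a baseline that the documents leave unsettled. Resumers are not drug-naive, and intolerable drug-related side effects are an exclusion, so a large restart effect cannot be presumed. Doses may be changed at any time, so continuers need not show zero change.

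Most of this stands, and it limits the point. Three stronger readings are tempting but not supported:

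- **That a planned early-AE table is misleading.** No such table is planned. The gap is that early events cannot be attributed.
- **That SAP 3.3.2 treats everyone as continuously on drug.** It claims only exposure before enrolment, which appears true of all entrants, since each has a Run-in dose.
- **That a randomised comparison is lost.** It is only unplanned, since records can still be linked to MSK-002 arm. It would compare resuming with continuing, both open label, among completers who chose to roll over, so randomisation protects it only in part.

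The reply does not remove the effect on changes from an entry baseline, which recurs at every visit. The listings do not help unless they carry MSK-002 group, and no title suggests that they do. Low precision is a reason for caution in reading the columns, not for leaving them out of a descriptive study.

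**Conclusion.** The point holds as a cheap improvement, of minor to moderate weight. Under the baseline that the SAP indicates, pooled changes in vital signs and ECG would show 1/3 to 1/2 of the effect in resumers. That figure assumes an ex-placebo share of 1/3 to 1/2, no mean change in the other entrants, and resumption of drug at entry, which is inferred. With MSK-002 Day 0 as baseline, this part largely falls away. Whole-study AE incidence is little affected either way. What remains in both cases is that AEs soon after entry cannot be assigned to resuming or continuing drug. A split would inform that question but not settle it: about ±21 to 29 percentage points in MuSK-MG under the assumed sizes and rates.

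**What to change.** 1. State one safety baseline, and reconcile SAP 3.1.2, SAP 3.5, protocol 11.1 and the asterisked footnote to protocol Table 1 to it.
2. In SAP 3.1.4, add MSK-002 group (amifampridine, placebo, not randomised) as a descriptive by-variable within MuSK-MG, applied to changes from baseline in vital signs (T17) and ECG (T19).
3. Add one table, with the same columns, of TEAEs and drug-related TEAEs with onset from the first MSK-003 dose to Month 3. Protocol 9.1 collects non-serious AEs from the end of the double-blind study, while Table 1 footnote f starts at the first MSK-003 dose. These should be reconciled so that the start of the window is clear.
4. List AChR-MG patients individually with their MSK-002 group, since columns of about 5 would not be informative.
5. Do no testing, and note that the comparison is limited to completers who rolled over.

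The cost is a merge of the MSK-002 arm code, some extra columns and one new table. The downside is small columns that could be over-read. This concerns display only: it needs no change in visits or data collection and says nothing about dosing at entry.

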3.3 Safety Analysis

3.3.1 *General*

All safety summaries will be presented overall for the safety population. The evaluation will take into account the recorded adverse events (AE), clinical laboratory tests, vital signs, physical exam, ECG assessments and concomitant medications.

3.3.2 *Adverse Events*

Since patients started taking study medication before enrolled the study, all AE reported are considered as treatment-emergent adverse events (TEAE).

Tabular summaries will be provided by indication for the number and percentage of patients with:

- Any TEAE by SOC and PT. This summary will include the number of unique events reported.
- Any study drug-related TEAE by SOC and PT
- Any TEAEs by SOC, PT and maximum severity
- Any treatment-emergent serious adverse event (TESAE) by SOC and PT
- Any TEAE that results in patient discontinuation from the study by SOC and Preferred Term (PT)

A listing of all adverse events will be provided. In addition, separate data listings will be presented for the following:

- Patient deaths

- Serious Adverse Events (SAEs)
- Listing of Grade 3 (Severe) or Grade 4 (Life-threatening) AEs
- Listing of AEs leading to study discontinuation

3.3.3 *Vital Signs*

A summary of values and changes from Baseline will be provided by vital signs parameter and visit of at 3, 6, 9, 12, 15, 21, 27, 33 and 39 months.

3.3.4 *Electrocardiogram (ECG)*

Each over-read ECG interval and change from baseline in each interval will be summarized descriptively by visit at 3, 6, 9, 12, 15, 21, 27, 33 and 39 months

Treatment-emergent cardiac abnormalities, as well as the overall interpretation, will be summarized. Treatment-emergent ECG findings considered by the investigator to be clinically significant will be presented only in a listing.

3.3.5 *Clinical Laboratory Assessments*

A summary of laboratory values and changes from Baseline will be provided by test and visit of at 3, 6, 9, 12, 15, 21, 27, 33 and 39 months. In addition, laboratory measures out of range or abnormal will be presented for each visit. Values deemed clinically significant by the Investigator will not be summarized, but will be presented in a listing.

3.3.6 *Physical Examinations*

The number and percent of patients with physical examination abnormalities will be summarized by body system and visit of at 3, 6, 9, 12, 15, 21, 27, 33 and 39 months.

3.3.7 *Concomitant Medications*

A detailed listing of any concomitant medication taken by a patient during the course of the study will be provided. All medications, including those taken prior to study drug administration, will be listed by indication and sorted by patient and medication start date.

The following summaries will be provided by drug class and WHODRUG preferred term:

- Prior medications (medications started prior to taking study medication),
- Concomitant medications (medications started during study treatment),
- Ongoing medication (medications given during treatment, and still ongoing after completed study).

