PROTOCOL NUMBER: MSK-003
STUDY SITES: Up to 20 sites in USA and Europe
PHASE OF DEVELOPMENT: Phase 3
STUDY RATIONALE: The purpose of this study is to evaluate the long-term safety and tolerability of amifampridine phosphate in patients with MuSK antibody positive and AChR antibody positive myasthenia gravis (MG) patients who participated in the MSK-002 study.
OBJECTIVES: Primary 
• To characterize the long-term safety and tolerability of amifampridine phosphate in patients with MG Secondary 
• To assess the clinical efficacy of amifampridine phosphate over time in patients with MG based on change in Myasthenia Gravis Activities of Daily Living Score (MG-ADL)
STUDY DESIGN AND PLAN: This is a long-term extension study for patients who participated in Protocol MSK-002 where the efficacy and safety of amifampridine was evaluated, in patients diagnosed with MuSK-MG or AChR-MG. The planned duration of participation for each patient is at least 9 months (i.e. until amifampridine is approved by Regulatory Agencies for the treatment of MG or the development program is discontinued for this indication). All patients who have completed study MSK-002 and sign an informed consent may enroll in the long-term study. Those patients who demonstrated benefit after completing the dose titration period but failed to meet the randomization criteria on Day 0 of MSK-002 may also be eligible for this study. The evaluations for MSK-002 can serve as baseline for the Long-Term study, if available

The optimal dose and schedule for amifampridine from the end of the Run-in Period from Study MSK-002 will initially be used for each patient. The Investigator may adjust the dose of amifampridine during the course of this trial, in order to optimize neuromuscular benefit for the patient. Clinic visits for safety assessment and for evaluation of MG-ADL will be made at Months 3, 6, 9, 12, 15, 21, 27, 33 and 39. Additional visits may occur at the discretion of the Investigator.

NUMBER OF PATIENTS PLANNED:

Up to about 60 MuSK-MG patients and approximately 10 AChR-MG patients will be studied.

CRITERIA FOR INCLUSION AND EXCLUSION:

Individuals eligible to participate in this study must meet all the following inclusion criteria:

1. Participated in the MSK-002 study
2. Willing and able to provide written informed consent after the nature of the study has been explained and before the start of any research-related procedures.

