1.2 Design

The study will enroll those patients who have completed the MSK-002 study and after all final evaluations for that study have been completed, or those who demonstrated benefit after completing the dose titration period but failed to meet the randomization criteria on Day 0 of MSK-002.

The duration of participation for each patient is expected to be at least 9 months as patients may continue in the study until amifampridine is approved by Regulatory Agencies or the clinical development of amifampridine is terminated for this indication. In addition to amifampridine, patients will continue to receive previous concomitant medications, as needed.

After a new informed consent is signed and inclusion / exclusion criteria for the current protocol are satisfied, eligible patients will be given the optimal dose and dosing schedule that was identified in the Run-in Period from Protocol MSK-002.

The findings from the physical exam (including vital signs, weight); 12-lead ECG; clinical laboratory test results (including pregnancy testing) and any ongoing adverse events will be used as the baseline for the long-term safety evaluation.

The only efficacy measurement is the MG-ADL which will be completed every 3 or 6 months. Safety and tolerability assessments will be made every 3 or 6 months or more frequently at the discretion of the Investigator. The study will continue until amifampridine is approved by Regulatory Agencies or until development of the product for this indication is halted or until month 39 is reached. The Investigator may alter the dose and dosing frequency during the Long-Term Study as well as schedule additional clinic visits for any reason.

Patients will be seen in the clinic at the end of Months 3, 6, 9, 12, 15, 21, 27, 33 and 39. In between the 3-or 6-month visits, patients may also have telephone/video contact with the site, or unscheduled visits, if needed.

Any unused medication must be brought back to the clinic at each visit for drug accountability, and an additional supply will be dispensed.

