3. STATISTICAL METHODS

3.1 General

All data will be analyzed using the Statistical Analysis System (SAS®; Version 9.2 or higher).

Continuous variables will be presented by descriptive statistics: n, mean, standard deviation, median, minimum, and maximum. Categorical variables will be tabulated by frequency count and percentage. No hypothesis testing will be performed.

3.1.1 *Display of Decimal Places*

Means and medians will be reported to one decimal place more than the original unit reported on the case report form (CRF) or by the laboratory/vendor. Standard deviations will be reported to two decimal places more than the original unit. Minimum and maximum values will be reported to the same number of decimal places displayed on the CRF or by the laboratory/vendor.

3.1.2 *Visit Windowing*

For Vital signs, ECG, Lab and physical exam, the following protocol-specified visits are further defined for summary tables as below.

- Screening Visit (Baseline): the day subject was screened following the ICF signing
- Follow-up visit (3 Months): the visit date was most close to 91 days after baseline visit.
- Follow-up visit (6 Months): the visit date was most close to 183 days after baseline visit.
- Follow-up visit (9 Months): the visit date was most close to 274 days after baseline visit.
- Follow-up visit (12 Months): the visit date was most close to 365 days after baseline visit.
- Follow-up visit (15 Months): the visit date was most close to 456 days after baseline visit.
- Follow-up visit (21 Months): the visit date was most close to 640 days after baseline visit.
- Follow-up visit (27 Months): the visit date was most close to 822 days after baseline visit
- Follow-up visit (33 Months): the visit date was most close to 1005 days after baseline visit
- Follow-up visit (39 Months): the visit date was most close to 1187 days after baseline visit

For completed subjects, Follow-up visit (39 Months) is considered End of study visit.

For discontinued subjects, if the assessments at the scheduled visit prior to the early termination (ET) visit were not done, the ET visit will be assigned as the prior scheduled visit. Otherwise, the ET visit will be assigned to the next scheduled visit.

Other visits will be listed as “Unscheduled Visits”, and data collected at unscheduled visits will not be included in the summary table, but will be presented in the data listings.

3.1.3 *Missing Data Handling*

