3.4 Analysis Report

Multiple interim analyses may be conducted upon requested. For example, the annual development safety update report (DSUR) and/or 120 Day safety update. The final study report will be conducted after study completed. One database lock is planned for this study at the end of the study.

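### Adverse events are summarised only as whole-study percentages, with no patient-year rate or breakdown by time, although follow-up may run from about 9 to 39 months

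*SAP*

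**What the plan says.** SAP 3.3.2 sets the form of the AE tables: "Tabular summaries will be provided by indication for the number and percentage of patients with" any TEAE, a drug-related TEAE, TEAEs by maximum severity, a serious TEAE, or a TEAE leading to discontinuation. The any-TEAE table also counts unique events. SAP 3.3.1 presents safety summaries overall. The visit windows in SAP 3.1.2 cover vital signs, ECG, laboratory tests and physical examination, and SAP 3.3.3 to 3.3.6 summarise these by visit. AEs have no window or interval.

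On length of follow-up, SAP 1.2 says: "The duration of participation for each patient is expected to be at least 9 months". The study runs until approval, "or until development of the product for this indication is halted or until month 39 is reached". On size, the protocol synopsis says: "Up to about 60 MuSK-MG patients and approximately 10 AChR-MG patients will be studied".

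On exposure, SAP 3.2.4 tabulates "The treatment duration (day), the total dose (mg) of study drug administered, average daily dose of study drug" and compliance. This is table T03, marked for both the study report and the development safety update report (DSUR). Neither document uses it as a denominator for AEs. The AE tables T06 to T10 are marked for both reports too, and SAP 3.4 gives examples of interim reporting: "For example, the annual development safety update report (DSUR) and/or 120 Day safety update".

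**The concern.** The primary objective is long-term safety and tolerability, and Protocol 13.3 words the primary endpoint by month, from Month 3 to Month 39. The percentage of patients who ever have an event grows with the time they are watched. If one patient contributes 9 months and another 39, the percentage mixes risk with length of observation. The study has a single arm, so no parallel group with similar follow-up helps a reader to interpret it.

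The second loss is timing. Three events in the first six months and three events after Month 21 would give the same line in the planned tables. For a long-term extension, that difference is much of what the study can show.

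**Working it through.** The plan states no AE rate, power or precision figure, so there is nothing to reproduce. The check has a reading part and an arithmetic part.

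**1. Reading.** I looked for a patient-year rate, a time to first event or an interval incidence in SAP 3.1 to 3.5, SAP 4.1 to 4.2 and Protocol 13.3 to 13.5. There is none. That the AE tables cover the whole study is inferred from SAP 3.3.1 and from the absence of any AE interval.

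**2. Range of follow-up.** Inputs are the planned group sizes (60 and 10) and the SAP 3.1.2 target days: "Follow-up visit (9 Months): the visit date was most close to 274 days after baseline visit" and "Follow-up visit (39 Months): the visit date was most close to 1187 days after baseline visit". Patient-years (PY) = n × days / 365.25.

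- MuSK-MG: 60 × 274 / 365.25 = 45.0; 60 × 1187 / 365.25 = 195.0.
- AChR-MG: 10 × 274 / 365.25 = 7.5; 10 × 1187 / 365.25 = 32.5.
- Ratio: 1187 / 274 = 4.3.

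**3. What one percentage can mean.** Event counts are hypothetical. Exact Poisson 95% limits for x events are χ²(0.025; 2x)/2 and χ²(0.975; 2x+2)/2, divided by PY. For x = 3 they are 0.619 and 8.767 events; for x = 1, 0.025 and 5.572; for x = 0, the upper limit is 3.689.

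| Planned table shows | Per 100 PY, all end at Month 9 | Per 100 PY, all reach Month 39 |
|---|---|---|
| MuSK-MG 3/60 (5.0%) | 6.7 (1.4 to 19.5) | 1.5 (0.3 to 4.5) |
| MuSK-MG 0/60 | upper limit 8.2 | upper limit 1.9 |
| AChR-MG 1/10 (10%) | 13.3 (0.3 to 74.3) | 3.1 (0.1 to 17.1) |

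**4. How far T03 closes the gap.** SAP 3.1 reports n and mean, so n × mean treatment duration gives total patient-years. Dividing patients with an event by that total leaves time after the first event in the denominator. The worst case is that all events fall on day 1.

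- For 3/60, 57 patients contribute time: 57 × 274 / 365.25 = 42.8 and 57 × 1187 / 365.25 = 185.2 PY. The rates become 7.0 and 1.6 instead of 6.7 and 1.5, an error of at most 60/57 − 1 = 5%.
- For 12/60 the same bound is 60/48 − 1 = 25%.

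The approximation is therefore close for uncommon events and poorer for common ones. It says nothing about timing.

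**5. Repeated reports.** Assume a constant first-event rate r (the documents give none), equal follow-up and cumulative tables. The percentage at t years is 1 − exp(−rt).

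| Assumed r per patient-year | 12 months | 24 months | 36 months |
|---|---|---|---|
| 0.1 | 9.5% | 18.1% | 25.9% |
| 0.2 | 18.1% | 33.0% | 45.1% |
| 0.4 | 33.0% | 55.1% | 69.9% |

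The risk is constant in every row.

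**6. SAE tail.** Protocol 9.2 collects serious AEs (SAEs) until 4 weeks after the last visit. That adds 28/274 = 10.2% to a 9-month follow-up and 28/1187 = 2.4% to a 39-month one.

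**The case against.** The strongest reply is that the study is descriptive, has one arm and tests nothing. SAP 2.2.1 defines its AE endpoints as the incidence of patients with an event, and a number with a percentage is exactly that. This stands: a reader might infer that the primary endpoint is left unanalysed or wrongly analysed, and the documents do not support that.

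A reader might also take the 4.3-fold range as uncertainty left in the final report. It is not. T03 will show the actual treatment duration, and step 4 shows that a pooled crude rate can then be approximated within about 5% for an event as rare as 3/60. Two gaps remain. Interval incidence cannot be recovered from the planned tables. A rate by MG type is not assured: SAP 3.1.4 requires the split for safety endpoints and SAP 2.2.1 does not list exposure among them, although Protocol 13.2 says safety will be evaluated separately by group.

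Patient-level listings are planned too (DL06a for AEs in both reports, DL10 for drug administration in the study report). With some 70 patients, a determined reader might rebuild more by hand. Their columns are not given, and a listing does not replace a summary. The table shells are not given either, so the content of T07 beyond its title cannot be checked.

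Finally, a reader might infer that DSUR percentages will rise from year to year. The SAP does not say whether those tables are cumulative or by period, and it makes interim analyses optional. Step 5 applies only if they are cumulative.

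**Conclusion.** The point holds as an improvement to the analysis of the primary objective. AEs, the leading safety measure, are the one main safety domain without any time resolution, and no planned AE summary accounts for how long patients were followed. For MuSK-MG the outer bounds are 45.0 and 195.0 patient-years, under which one and the same 3/60 corresponds to 6.7 or 1.5 per 100 patient-years. These bounds rest on the planned group sizes and the SAP visit days. They are not a forecast, and patients who leave before Month 9 would take the lower bound below 45.0. The event counts are illustrative.

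Reading T03 beside the AE tables removes much of the ambiguity for the pooled rate of uncommon events. It does not give timing, or with certainty a rate by MG type. If DSUR tables are cumulative, a rising percentage could reflect longer follow-up alone.

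**What to change.** Keep the number and percentage, and add to SAP 3.3.2:

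1. **Rates.** By MG type, for any, drug-related, serious, Grade 3 or higher and discontinuation TEAEs: patients with a first event per 100 patient-years at risk, with exact Poisson 95% CI.
2. **Timing.** Incidence by interval since the first MSK-003 dose, with boundaries at scheduled visits (for example 0–6, >6–12, >12–21 and >21–39 months) and the number at risk at the start of each. For AChR-MG, counts and numbers at risk are enough. Label the scale as time since MSK-003 entry: patients already took amifampridine in MSK-002, so it is not time since first exposure.
3. **One end of follow-up.** Use a single stated at-risk end date for all categories in the main rates, so that serious events remain a subset of any TEAE. The last visit is a natural choice, or death or a report's data cut-off if earlier. Show SAEs in the following 4 weeks as a separate count or sensitivity rate. State how this time relates to T03, which stops at the last dose, since Protocol 8.2.3 separates leaving treatment from leaving the study.
4. **Events counted.** Include in the rates events with onset on or after the first MSK-003 dose. Show events ongoing from MSK-002 separately.
5. **Exposure.** Present T03 by MG type with total patient-years.
6. **Interim reports.** State whether DSUR tables are cumulative or by period.

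The cost is SAP text, one time-to-first-event derivation, extra columns and a split of T03, before the single database lock. It uses AE onset, dose and visit dates. The downside is longer tables and very wide AChR-MG intervals, and the rate is a constant-risk summary that should be read beside the interval table.

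Two neighbouring matters are separate points: the differing start of non-serious AE reporting in Protocol 9.1 and Table 1 footnote f, which must be reconciled, and the mismatch between the SAP 4.1 output list and SAP 3.3.2.
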